### **Research Design:**

**Study Design-** Phase I of the proposed study will utilize an alternating treatment design (ATD) aimed at isolating the effects of an unstudied treatment component contained in several existing transdiagnostic treatments on putative mechanisms maintaining symptoms of emotional disorders. The role of acting inconsistent with emotion-driven behavioral urges (EDBs) in reducing the intensity of emotional experiences will be examined by rapidly alternating two experimental conditions (acting consistent vs. inconsistent with an induced emotion) within the individual. Phase II will also use a SCED (a multiple baseline approach) to explore whether a brief intervention focused solely on acting inconsistent to EDBs indeed leads to change in the frequency of EDBs and the intensity of experienced affect using real-time assessment techniques (EMA).

Clinician-rated, self-reported, and behavioral measures of BPD symptoms and emotional tolerance will also be administered weekly and/or at major assessment time-points (pre-baseline, pre-intervention, post-intervention, and post-follow-up). The baseline period (2 or 4 weeks in duration) will serve as the control condition, allowing us to observe whether change on variables of interest occur only when the intervention is applied. This project is very much in line with the PI's mentor's and collaborator's work developing and testing treatments for BPD ([name]) and investigating mechanisms of action in existing interventions ([name]).

**Study Setting:** All study sessions will be conducted at CARD, which is one of the largest research clinics devoted to emotional disorders in the world and maintains a substantial patient flow. The clinic consists of approximately 15,000 sq. ft. of space and includes multiple individual and group treatment rooms and full-time administrative staff including two receptionists covering the front desk during the 12-hour clinic day (8 a.m. through 8 p.m.). Staff members include licensed psychologists, a psychiatrist, a nurse, research technicians, doctoral students from clinical psychology and counseling psychology, and psychiatric residents.

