**PHASE II: Multiple Baseline with Phase Change Procedures:** Participants (8) will be randomized to a 2- or 4-week initial baseline period. The baseline period will consist of assessment only, described in detail below. Following the initial baseline period, participants will receive 4 weekly 50-minute sessions of an intervention; this duration of treatment is consistent with clinical experience at our center indicating that this is an adequate amount of exposure to given UP modules. The Countering EDBs Module from the UP will be used as the basis for session content as the modular approach of the UP allows for the delivery of just this treatment topic isolation. Randomization to baseline phases of differing lengths will allow us to explore whether change on variables of interest occurs when and only when the intervention is applied. *Phase II Treatment Quality Assurance.* The PI (applicant) will serve as the study therapist. The PI is a licensed clinical psychologist with over eight years of experience with adults with BPD. Additionally, the PI is fully certified as an expert in the delivery of the UP. All therapy sessions will be audiotaped and will all be rated for adherence and competence ratings by an expert rater. Most importantly for the current project, integrity measures will assess for allowed and disallowed techniques within the UP to ensure only information regarding countering EDBs is presented as a means to isolate this putative mechanism. Descriptive statistics on fidelity measures will be obtained.

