**Phase II Assessment Quality Assurance. Independent Evaluator (IE) Qualifications.** Clinician-rated measures (DIPD-R, ZAN-BPD, Mini-ADIS) will be administered by graduate level IEs at a pre-baseline period assessment, a pre-intervention assessment, a post-intervention assessment, and a post-follow up assessment. IEs will be trained to reliability on the DIPD-R and ZAN-BPD by the PI who will have previously completed training on these measures with [name], author of these measures and a collaborator on this project. Further, all graduate students at CARD receive rigorous training and meet strict certification criteria in the administration of the ADIS-5, which would be completed prior to their participation on the current study. For more information regarding this training process, see Brown and colleagues. *Reducing IE drift.* All assessments will be audio recorded and the PI will rate 15% of randomly selected interviews at regular intervals. If reliability falls below criteria, IEs will be retrained. Reliability statistics will be included in publications. Because all participants in Phase II will be in active treatment, it will not be necessary for IEs to remain blind. Additionally, we fully expect that some patients' BPD symptoms may not improve after only four sessions (as our primary focus is our ability to manipulate the putative mechanism of EDBS), thus reducing concerns about IE bias regarding the favorability of the intervention. **Data Entry Procedures.** Both patient self-report measures and IE measures will be completed directly on smart-phones (participant self-report) or tablet computers (IE entries) that will transfer data directly into secure databases using SymTrend's online survey program; this will greatly reduce human errors that occur by manually entering data. See Safety/confidential section for data safety information.

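### The reason given for leaving Phase II evaluators unblinded contradicts the untreated control baseline, and the drift check by the treating PI does not protect the exploratory clinician-rated ZAN-BPD

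*Combined protocol and SAP*

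**What the plan says.** The Phase II Assessment Quality Assurance section gives two reasons for not masking the IEs who score the clinician-rated ZAN-BPD. The first is "Because all participants in Phase II will be in active treatment, it will not be necessary for IEs to remain blind". The second is that some patients are not expected to improve in BPD symptoms after only four sessions, which is said to lessen concern about bias in favour of the intervention.

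Other sections describe the phases differently:

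- PHASE II: Multiple Baseline with Phase Change Procedures: "Participants (8) will be randomized to a 2- or 4-week initial baseline period", and "The baseline period will consist of assessment only".
- Study Design: "The baseline period (2 or 4 weeks in duration) will serve as the control condition".
- Participant Safety and Confidentiality: other treatment is to be avoided during baseline, treatment and follow-up alike.

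On who rates and who checks, the Multiple Baseline section says "The PI (applicant) will serve as the study therapist". The Quality Assurance section says that the PI trains the IEs to reliability on the ZAN-BPD, that assessments are audio recorded, and that "the PI will rate 15% of randomly selected interviews at regular intervals". IEs are retrained if reliability is too low; no threshold is given. No passage masks the IEs, or the PI as second rater, to visit or phase.

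**The concern.** In a multiple baseline design each participant is their own control, and the contrast of interest is untreated against treated phases. The absence of a separate untreated group does not remove the need for masking. The rater's knowledge of phase plays the part that knowledge of arm plays in a parallel-group trial. Phase II Hypothesis III predicts that BPD symptoms will fall only once the intervention is given, and a rater who expects benefit and knows the phase would tend to produce that pattern.

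The stated safeguard does not test for this. A drift check shows whether two raters agree. If the second rater is the therapist, who also trained the first and also knows the phase, good agreement is compatible with a bias that both share.

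At stake is the credibility of the only interviewer-rated evidence on BPD symptoms. The Timeline section foresees a larger efficacy application on the effect of the intervention on those symptoms.

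**Working it through.** **1. How much of Phase II is treatment.** Inputs: 8 participants and a baseline of 2 or 4 weeks (Multiple Baseline section), treatment of four weekly sessions ("participants will receive 4 weekly 50-minute sessions of an intervention"), and follow-up of 4 weeks (Study Overview). The split between baseline lengths is not stated. With k participants on the 2-week baseline, the person-weeks are

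10k + 12(8 − k) = 96 − 2k.

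The Power Analyses section gives 88 weekly and 616 daily observations. Setting 96 − 2k = 88 gives k = 4, and 88 × 7 = 616. The plan's own totals therefore reproduce exactly at a 4:4 split. They do so only when the untreated weeks are counted; without follow-up the total would be 4 × 6 + 4 × 8 = 56 weeks.

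At that split the 88 person-weeks divide as follows:

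| Phase | Person-weeks | Share |
|---|---|---|
| Baseline, no treatment | 4 × 2 + 4 × 4 = 24 | 27% |
| Treatment | 8 × 4 = 32 | 36% |
| Follow-up, treatment ended | 8 × 4 = 32 | 36% |

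**2. How many clinician ratings precede treatment.** The Phase II Assessment section and its table place the clinician-rated ZAN-BPD at pre-baseline, pre-intervention, post-intervention and post-follow-up. That is 8 × 4 = 32 ratings, of which 8 × 2 = 16 (50%) come before the first session. This count does not depend on the 4:4 split.

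**3. Whether phase reveals condition.** The Phase II Data Analyses section examines clinician-rated symptoms by baseline, treatment and follow-up. The visits sit at the phase boundaries, so the visit label identifies the condition.

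**4. What the drift check can show.** If the 15% is applied to these 32 interviews, it covers 0.15 × 32 = 4.8, about 5 recordings. For a simple random draw of 5 from 32 (201,376 possible draws):

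- No participant has both a pre-treatment and a post-treatment recording in 95,872 draws, or 48%.
- No participant has both the pre-intervention and the post-intervention recording in 169,680 draws, or 84%.

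Masking these recordings alone would therefore say little about within-person rater bias. The selection has to change as well.

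**5. Which outcomes are exposed.** Hypothesis I rests on self-reported emotion-driven behaviours, the PANAS, the MEAQ and the computerised PASAT-C. IEs score none of these. The clinician-rated ZAN-BPD appears only in Hypothesis III, which is labelled exploratory.

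**The case against.** The strongest reply is that the exposed outcome is exploratory, as both the Study Overview and the Phase II Data Analyses section say, and that the same construct is also self-reported weekly and at every major assessment. That stands, and it limits the point. A reader might infer that the main Phase II conclusions are compromised. The documents do not support that, because this route does not reach the Hypothesis I outcomes.

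A second reply is that the sponsor considered bias and gave a further reason, the expected lack of improvement in some patients. It shows the matter was not overlooked, but it leaves expectations about the other patients in place and sits awkwardly with Hypothesis III.

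A third is that the drift check has real strengths: the PI is trained by the measure's author, interviews are chosen at random, and reliability will be published. Nor does the plan say that PI scores replace IE scores, so it would go too far to say that the therapist sets the outcome scores. What remains is that the only named comparison rater is the treating PI, with no masking stated.

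One might also argue that everyone is eventually treated, so there is no arm to conceal. That does not answer a comparison between phases. It is right, though, that baseline length itself needs no masking: knowing whether baseline lasted 2 or 4 weeks does not tell a rater which phase is being scored.

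**Conclusion.** The concern holds within a narrow scope. The first rationale for unblinded IEs is contradicted by the assessment-only control baseline: half of the planned clinician-rated ZAN-BPD interviews precede treatment. The reliability check cannot expose a bias shared by the IEs and the treating PI. The consequence is confined to an exploratory outcome.

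The size of any bias is unknown. As an illustration only, in a two-sided 5% paired t-test with 8 participants (7 df, noncentrality = shift × √8) and no true change, an assumed rater shift of 0.2, 0.3 or 0.5 SD of the change score would raise the false-positive rate to about 8%, 11% or 23%. A reader might take these as the plan's error rates. They are not: the shift is assumed, and the plan specifies no t-test or significance level for this outcome. The randomization tests planned for the other outcomes would not remove a bias that follows phase either.

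The verdict assumes that the 15% check applies to the ZAN-BPD interviews. The count of 16 in 32 needs no assumption beyond the planned visits being completed.

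**What to change.** 1. Delete the statement that IEs need not be blind, with its active-treatment rationale.
2. Do not tell IEs the visit label, and assign the available IEs to visits in random or balanced order. Barring whoever did the eligibility interview from all later visits would not be a good substitute: the pre-baseline score would then always come from a different rater than the later scores, confounding rater with time.
3. Have the existing audio re-rating done by an IE who did not conduct that interview, in shuffled order and masked to time point, instead of by the treating PI. Select matched pre-intervention and post-intervention recordings from the same participants rather than a simple random 15%. Three pairs are 6 recordings against about 5 now; all eight pairs are 16. Use the result as an agreement check, and as a phase-effect estimate only if all pairs are re-rated.
4. Report the clinician-rated ZAN-BPD as exploratory and incompletely masked, beside the self-report version.

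The cost is some scheduling effort and a few more re-rated recordings, with no new visit. No new staff are needed if at least two IEs are trained; the plan uses the plural but gives no number. Masking will be imperfect. Participants may mention therapy, the assessment table places the diagnostic interviews only at pre-baseline, and the Participant Retention section names IEs among those to whom participants first bring concerns. The pre-intervention and post-intervention visits carry the same measures in the table, which is a further reason to pair those two.

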**PHASE 1: ATD Component Procedures.** Twenty-four participants will be included in the ATD component of this study. There are four discrete emotions (anger, sadness, anxiety, and guilt) under investigation and participants will be randomly assigned to complete study procedures for only one emotion. Six participants will be assigned to each emotion condition. Following usual and customary procedures for ATDs, the first participant for each discrete emotion will comprise the main experiment with the subsequent participants serving as replications. Each participant will be presented with six emotion inductions (focused on the emotion related to their assigned condition), occurring on six separate days over the course of two weeks. In order to maximize clinical relevance, emotional stimuli used in the emotion inductions will be tailored to each individual by instructing participants to write about a time in the past two months in which they felt the particular emotion being induced. This strategy has been successfully implemented previously by the PI to induce strong emotions in individuals with BPD. Prior research has suggested that using idiographic stimuli (vs. standardized stimuli) results in greater emotional reactivity in individuals with BPD and anxiety disorders. Prior to the first emotion induction in the first session, study staff will assist participants in developing a list of situations, occurring in the past two months, that brought up the emotion consistent with the condition to which the participant is assigned. Participants will be asked to rate the emotional intensity of each situation (on a 1-100 scale consistent with subjective units of distress) and six situations rated above 60 (to ensure sufficiently strong emotion is induced) will be chosen as the basis for the emotion induction writing assignments.

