Following each emotion induction, participants will be instructed to either act consistent or inconsistent with the emotion induced; instructions will be randomly alternated so that each participant will act consistent during 3 sessions and act inconsistent during 3 sessions. The randomization schedule will be such that one condition will not be presented more than two times in a row. Participants will be informed that “the goal of this project is to test out two different strategies for coping more effectively with emotions in order to ascertain the most effective strategy for you.” The two conditions will both be presented as credible and effective strategies to the participants in order to minimize any biased results due to expectancy effects. The specific instructions for acting inconsistent and consistent with EDBs following the mood induction will be based on idiosyncratic action urges associated with the induced emotions. For example, the guilt induction may elicit action urges to withdraw/hide and/or (albeit less commonly) lash out in an effort to deflect blame. Acting inconsistent to urges to withdraw may involve making plans with friends (via phone or email) or making small talk with confederates while acting inconsistent to urges to lash could include writing thank you notes to loved ones or engaging in an act of kindness. Study staff will assess for idiosyncratic emotion-driven action urges after the emotion induction to craft appropriate behavioral instructions relevant for the individual.

An important advantage of SCEDs is that the flexible nature of these studies and the immediate availability of results allows for the real-time alteration of procedures in order to obtain an effect on the putative mechanism of action. In this case, if we fail to find reductions in the intensity of the induced emotion by asking participants to act inconsistent with their reported action urges, we may, for example, extend the purview of behaviors to include emotion-consistent/inconsistent posture, and tone of voice. Making these changes informs the development of interventions by evaluating various strategies to manipulate putative mechanisms. The strategies tested can be confirmed by replication and also associated with individual characteristics. Participants will be paid \$40 per session for a total of \$240 for completing the entire six study sessions.

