*Phase I Assessment.* The DIPD-IV and ADIS-5 (described above) will be used to confirm inclusion and exclusion criteria. The primary dependent variable in Phase I is the intensity of the discrete emotion induced.

Three convergent indices (self-report, behavioral, and physiological) will be used. **Self-report:** The Positive and Negative Affective Schedule-Expanded Form (PANAS-X) includes subscales measuring the intensity of the four discrete emotions represented in this study (fear, sadness, guilt, and anger). A Manipulation Check will be included asking participants to rate the extent to which they feel they were adherent to the prescribed strategy (acting consistent vs. inconsistent). **Behavioral:** The Facial Expression Coding System^58 (FACES) is a rater-coding system that yields information regarding the frequency, intensity, and duration of facial expressions. Participants' facial expressions will be video recorded throughout all study procedures and all tapes will be subsequently coded by trained undergraduate research assistants. The applicant will receive standard training in this protocol by [name], its creator and a collaborator on this project.

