**DATA ANALYSIS: PHASE I & II.** *Phase I Data Analyses:* Hypotheses regarding differential outcomes between the two strategies (acting consistent versus inconsistent) will be evaluated using a combination of classical methods of idiographic data-analysis and modern non-parametric statistical techniques. We will first plot parallel lines representing intensity of emotion as a function of each individual strategy. These will be directly compared as to changes in level and slope. In addition to customary visual observation (often, functions in ATDs yield non-overlapping datasets), more quantitative evaluations will also be employed by conducting non-parametric randomization and bootstrap tests of the mean differences between the two conditions. The non-parametric statistical analyses will be conducted using the Single-Case Randomization Tests package (SCRT) within the R statistical framework. Randomization tests will be conducted regarding levels of mean change in self-reported emotional intensity and clinician-rated facial emotional intensity from post-induction to post-regulation condition (acting consistent/inconsistent). Results from these non-parametric randomization tests will be used in conjunction with the visual observations for each individual to draw conclusions regarding the effect of acting counter to EDBs on the intensity of emotion relative to acting consistent with emotional urges.

*Phase I, Hypothesis 1:* When instructed to respond to induced emotions by acting inconsistent to emotional urges, participants will demonstrate greater reductions in the intensity of their emotions compared to acting consistent with their emotional urges. Similar patterns of results are expected across all discrete emotions induced.

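### Phase I does not state the unit of its randomization test: run per person, only 14 orders are allowed and two-sided p cannot reach 0.05, and no pooled test or combining rule is described

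*Combined protocol and SAP*

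**What the plan says.** Under PHASE 1: ATD Component Procedures, 24 people are assigned six to each of four emotions, and each has six induction sessions on separate days. The design is that "each participant will act consistent during 3 sessions and act inconsistent during 3 sessions", with the restriction: "The randomization schedule will be such that one condition will not be presented more than two times in a row". Within an emotion, "the first participant for each discrete emotion will comprise the main experiment with the subsequent participants serving as replications".

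Under DATA ANALYSIS, Phase I combines idiographic methods with randomization and bootstrap tests of mean differences, run in a single-case randomization package. On outcomes: "Randomization tests will be conducted regarding levels of mean change in self-reported emotional intensity and clinician-rated facial emotional intensity". On inference: "Results from these non-parametric randomization tests will be used in conjunction with the visual observations for each individual to draw conclusions". Hypothesis 1 is directional and adds: "Similar patterns of results are expected across all discrete emotions induced". The section gives no unit of analysis for either kind of test, no alpha, no sidedness, no probabilities for the allowed orders, and no pooled statistic or rule for combining participants.

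The Phase I Assessment section says the self-report instrument "includes subscales measuring the intensity of the four discrete emotions represented in this study", so the outcome subscale differs by assigned emotion. Power Analyses equates sample size with number of observations, counts them per emotion and in total, and states that medium effects will be detectable.

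**The concern.** The text points two ways on the unit. The idiographic framing, the single-case package and the replication design suggest one test per participant. The observation counts under Power Analyses suggest combined data.

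On the first reading, a randomization test can be no finer than its set of possible orders, and six restricted sessions give very few. The p-value could then not separate a medium effect from no effect at a conventional two-sided level, and nothing says how many replications would support Hypothesis 1. On the second reading, the analysis section describes no test that uses participants together and no common scale for four different subscales.

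On either reading, the detectability statement is not attached to a described analysis. The gap matters more because the design "allows for the real-time alteration of procedures in order to obtain an effect on the putative mechanism of action": with unit, level and combining rule left open, these choices could be made after results are seen.

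**Working it through.** **1. The plan's own counts.** Inputs from PHASE 1: ATD Component Procedures: 24 people, 6 per emotion, 6 sessions each, 3 per condition.
- Per emotion: 6 × 6 = 36, or 18 + 18. The plan states 35 but also 18 and 18.
- Total: 24 × 6 = 144, or 72 per condition. The plan states 180 and 90. A total of 180 would need 30 people (180/6) or five emotions of 36, so it is not reproduced.

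**2. Allowed orders for one person.** Balanced orders: C(6,3) = 20. Full enumeration leaves 14 with no run longer than two. Swapping the condition labels maps this set onto itself, so each mean difference has a mirror image of equal size.

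**3. Smallest attainable p for one person.** The one-sided minimum is the probability of the observed order. The two-sided minimum is twice that. The plan does not say how orders are drawn, so three methods are shown.

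| How orders are drawn | Order probabilities | One-sided floor | Two-sided floor | Share of participants for whom one-sided p ≤ 0.05 is possible |
|---|---|---|---|---|
| Equally likely | 1/14 each | 1/14 = 0.071 | 2/14 = 0.143 | 0% |
| Fair choice at each session where both conditions are open | 1/8 (4 orders), 1/16 (6), 1/32 (4) | 1/32 = 0.031 | 2/32 = 0.0625 | 4/32 = 12.5% |
| In proportion to remaining slots | 1/20 (6 orders), 3/40 (4), 1/15 (2), 2/15 (2) | 1/20 = 0.05 | 2/20 = 0.10 | 6/20 = 30% (p exactly 0.05) |

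The two-sided floor exceeds 0.05 in every row, so per-person power at two-sided 0.05 is 0% for any effect size.

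**4. Per-person power at looser settings** (simulated; normal residuals with SD 1). At one-sided 0.05 and a 0.5 SD effect: 0% with equally likely orders, 2% with fair choices, 5% with proportional draws. At one-sided 0.10 with equally likely orders: 17% at 0.5 SD, 32% at 1 SD, 69% at 2 SD.

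**5. A pooled test on the same data.** Sum the standardized mean differences over participants and re-randomize each person among the 14 orders. For one emotion there are 14^6, about 7.5 million, arrangements, so the floor is no longer a constraint. Assumptions: common shift of 0.5 SD, independent sessions, no trend, two-sided 0.05.

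| Setting | Simulated rejection rate |
|---|---|
| 24 people | 84% |
| 12 people | 52% |
| 6 people (one emotion) | 30% |
| 24 people, effects vary between people with SD 0.5 | 78% |
| 24 people, effects vary with SD 1.0 | 66% |
| 24 people, linear drift 0.4 SD per session | 69% |
| 24 people, no effect in anyone | about 5% |
| 24 people, zero average effect, SD 0.5 | about 8% |
| 24 people, zero average effect, SD 1.0 | 14–15% |

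A normal approximation agrees. With 72 sessions per condition, SE = √(2/72) = 0.167, 0.5/0.167 = 3.0, and power ≈ Φ(3.0 − 1.96) = 85%. With 18 per condition, SE = √(2/18) = 0.333, 0.5/0.333 = 1.5, and power ≈ Φ(1.5 − 1.96) = 32%.

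**6. Limit of the pooled test.** With a 2 SD effect in one emotion and none in the other three, it still rejects 52% of the time. Rejection therefore does not show similar effects across emotions.

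**The case against.** The floor depends on three things the documents do not state: a per-person unit, a 0.05 level and a two-sided test. In the sentence on inference, the reference to each individual grammatically attaches to the visual observations rather than to the tests. Hypothesis 1 is directional, so a one-sided test is natural, and under session-by-session draws one-sided p of 0.05 or less is possible for some orders. All of this stands, and it is why the point is conditional.

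A reader might go further and infer that Phase I cannot support any conclusion on Hypothesis 1. The documents do not support that. The tests are read alongside visual inspection, five replications per emotion are planned, and nowhere must one participant's p reach a threshold. Consistent direction across replications could still be informative, although no replication count is stated.

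It is also fair to say that making a group test the sole test of the hypothesis, or naming one primary outcome in place of the planned convergent indices, would be a preference and not a correction. The design is deliberately idiographic, and the pooled test cannot establish the part of Hypothesis 1 about similar patterns.

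Finally, the 84% rests wholly on assumptions, because the documents give no SD, drift or numerical medium effect. With between-person SD 1.0 and drift of 0.4 SD per session together, power is about 56%. With a 0.3 SD shift and neither complication, it is about 43%.

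**Conclusion.** The concern holds in conditional form and should be fixed. It is certain that the Phase I analysis leaves the unit, level, sidedness and combining rule unspecified. The order count and floors follow exactly from the stated design once a method of drawing orders is assumed. On the per-person reading, which the text favours without fixing it, no effect of any size can reach two-sided 0.05. One-sided 0.05 is out of reach with equally likely orders and reachable for only 12.5% or 30% of participants under the two sequential methods.

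The detectability statement therefore fails for per-person tests at two-sided 0.05, and on the combined reading it has no described test behind it. The data already planned could support a pooled test with reasonable power for a medium average effect under the stated assumptions, but not within a single emotion.

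**What to change.** Keep the individual plots, effect sizes and replication logic. Add to the Phase I Data Analyses a randomization test stratified by participant over all 24 people:

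- Re-randomize each person only among the 14 allowed orders, using the probabilities with which orders are actually drawn, and state how they are drawn.
- Put differences on a common scale across the four PANAS-X subscales, for example by dividing by a within-emotion SD computed without regard to condition.
- Run it for each planned index (self-report and facial coding), and state the level and sidedness.
- Repeat it within each emotion as a secondary analysis, noting power of about 30% for six people at 0.5 SD.
- Tie the detectability statement under Power Analyses to this test and its assumptions: about 84% for 24 people, 66% if effects vary between people with SD 1.0.
- State the floor for any individual p-value reported. State also that the pooled test addresses the null of no effect in any participant and does not by itself show similar effects across emotions.

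The cost is a paragraph and a few lines of R, with no new participants, visits or data. The downsides are a little more analysis work, a group-level result beside the idiographic one, low within-emotion power, and rejection above 5% (about 15% at SD 1.0) if effects vary around a zero average.
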